### 6.1 Intention-To-Treat population (ITT)

The ITT population includes all subjects who:

1. Are randomised, and
2. Receive at least one dose of MBGS206 study medication, and
3. Provide a baseline (see section 8.1.5 for full definition of baseline) primary endpoint safety value (lumbar spine) and at least 1 available evaluation of primary endpoint safety value (lumbar spine) post- Baseline in MBGS206.

Subjects will be analysed according to the treatment to which they were randomised.

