9.1.2 Schedule of Assessments

The schedule of assessments is presented in [Table 9–1](#).

Table 9–1 Schedule of Assessments

Visit		Treatment Period								
		1	2	3	4	5	6	7 (EOT)	8 (FU)	
Week	Assessments transferred from MBGS205	MBGS206 Baseline ¹ W24	W28 (±2 D)	W32 (±2 D)	W36 (±2 D)	W40 (±2 D)	W44 (±2 D)	W48 (±2 D)	W60 (±2 D)	
Confirmation of written informed consent		X								
Medical/surgical history	X									
Inclusion/exclusion criteria		X								
Treatment allocation ²		X								
Full physical exam: general, prostate and breast exam	X				X			X		
Limited physical exam			X	X		X	X		X	
Blood pressure (SBP, DBP) and heart rate	X		X	X	X	X	X	X	X	
12-Lead ECG	X				X			X		
Clinical laboratory tests³: haematology, blood chemistry, and dipstick urinalysis ⁴ , eGFR by Cockcroft-Gault formula, PSA	X		X	X	X	X	X	X	X	
Cardiometabolic parameters³: HbA1c, fasting lipids (total cholesterol, LDL, HDL, triglycerides), fasting glucose and insulin, hs-CRP, HOMA-IR	X							X		
Bone turnover markers⁵	X				X			X		
Testosterone total ⁶	X		X	X	X	X	X	X	X	
Testosterone bioavailable, oestradiol (total), SHBG, FSH, LH ⁶	X							X		
Semen PK ⁷	X							X		
Plasma PK ⁷	X							X		
Weight, BMI hip and waist measurement	X				X			X		
Body composition using bioimpedance ⁸	X				X			X		
Actigraphy ⁹	X							X		
Grip strength	X				X			X		
PROs: IIEF, BFI, SF-36 QoL PROMIS: SexFS, Fatigue Short Form PGI-S ¹⁰	X				X			X		
DEXA ¹¹	X							X		
Study drug dispensation		X	X	X	X	X	X			
Study drug administration ¹²										
Study drug accountability		X								

Visit		Treatment Period							
		1	2	3	4	5	6	7 (EOT)	8 (FU)
Week	Assessments transferred from MBGS205	MBGS206 Baseline ¹ W24	W28 (±2 D)	W32 (±2 D)	W36 (±2 D)	W40 (±2 D)	W44 (±2 D)	W48 (±2 D)	W60 (±2 D)
AE assessment ¹³	X		X	X	X	X	X	X	X
Concomitant medication	X		X	X	X	X	X	X	X

- 1 Baseline assessment will be performed on a same day as the EOT visit of Study MBGS205. As applicable, EOT assessments of Study MBGS205 will be used for Baseline assessments of Study MBGS206 and do not need to be repeated. The results of liver enzymes, PSA, haematocrit, and ECG assessments performed at the Baseline visit will not be available for eligibility assessment, therefore results of these parameters from last valid visit of Study MBGS205 will be used. This includes any of these parameters from last scheduled or unscheduled visit measure but no longer than 1 month before Baseline visit/EOT of MBGS205.

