9.3.4 Study Drug Interruption and Discontinuation

Subjects may voluntarily discontinue investigational treatment for any reason at any time.

At the time of study drug discontinuation, the subject should have (as soon as possible) an EOT visit with the assessments that are normally done at the Week 48 visit (EOT, Visit 7). This should take place within 7 days after discontinuation of study drug. The reason for the discontinuation must be documented in the subject's medical records and entered on the appropriate electronic case report form (eCRF) page. All subjects who discontinue the study drug should enter the FU phase and attend the final follow up visit 12 weeks after EOT (FU, Visit 8).

Subjects will in addition be asked to provide a plasma and semen sample for PK at EOT (Visit 7), unless they are not able to provide this sample. This applies also to a subject discontinued because of elevated testosterone as determined by an unblinded physician. The investigator and study staff must discuss with the subject, the subject's continued participation in the study and request subjects to continue attending FU visits according to the study visit schedule.

If the subject cannot, or is unwilling to attend the FU visits, the site staff should request maintenance of regular phone contact with the subject, or with a person pre-designated by the subject. This phone contact should preferably be performed according to the study visit schedule. Data concerning the subject's health status, including information regarding new/concomitant treatments, AEs, AESIs (i.e., rash), and vital status will continue to be collected.

The investigator must also contact the IRT to register the subject's discontinuation from investigational treatment.

If the subject temporarily discontinues study drug because of AE or SAE or other relevant issue, the investigator should attempt to restart it as soon as possible after circumstances allow and in agreement with the Medical Monitor.

Investigational treatment MAY be permanently discontinued under the following circumstances:

1. Significant worsening of lower extremity oedema
2. Significant worsening of obstructive urinary symptoms

Investigational treatment MUST be permanently discontinued under the following circumstances:

3. If subject develops fragility fracture.

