12.4 DEXA Scan

Bone density will be evaluated with standard procedure described in study imaging manual. All evaluations during the study for particular subject should, where possible, be performed on the same machine with particular attention to ensuring consistency in positioning patients.

To assess the spine, the subject will be in supine position with legs supported on a padded box to flatten the pelvis and lower (lumbar) spine. To assess the hip, the foot is placed in a brace that rotates the hip inward. The detector will be slowly passed over the area separately for spine and hip, generating images. The duration of examination will be up to 30 minutes. DEXA T Score will be calculated based on actual measured bone density value. Both values will be evaluated for safety.

EOT DEXA scan: If the subject is discontinued from the treatment early, DEXA will be performed only if they reached minimum Week 36 (Visit 4) active treatment period. In order to accommodate scheduling, EOT DEXA can be performed within 5 days before the EOT visit

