13.3.1 Intention to Treat

The ITT population includes all subjects who:

1. Are randomised, and
2. Receive at least 1 dose of study medication, and
3. Provide a Baseline efficacy value and at least 1 available evaluation of efficacy post-Baseline.

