- 7 All subject that are not vasectomised will be asked to provide a semen sample. Subjects that provided semen sample for PK will also have plasma for PK drawn at the assessment visit Semen sample collection is not required to be the same day as the assessment visit. Therefore, semen PK collection is allowed  $\pm$  48 hours around the plasma PK attendance visits.
- 8 Subjects should come well hydrated, drinking water the night before and the morning before the impedance measurements
- 9 Activity wrist monitors will be collected from subjects at EOT visit of the Study MBGS205. If the activity wrist monitor was not performed before EOT of Study MBGS205 and collected at EOT Study MBGS205, it can be applied at the Baseline visit of current study and worn for 7 c consecutive days and collected at Visit 2. An activity wrist monitor will also be worn for 7 continuous days after Visit 7 (EOT) and collected at Visit 8 (FU)
- 10 Some questionnaires will be new for some subjects and completed first time at the Baseline visit
- 11 For subjects that discontinued early, EOT DEXA scan will be performed only if they reached minimum Week 36 (Visit 4) active treatment period. In order to accommodate scheduling, EOT DEXA can be performed within 5 days before the EOT visit
- 12 First dose of study drug will be administered at the site at Baseline visit
- 13 AEs, SAEs, and AESIs collected from signature of informed consent.

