## 7.2 Handling of missing data and outliers

### 7.2.1 Missing data analysis methods

Unless specified, data in summary tables will be presented using Observed Case (OC) data and therefore no missing data will be imputed.

For specified endpoints a last observation carried forward (LOCF) imputation will be utilised. In this approach subjects with a missing observed value at a visit will be imputed with the last non-missing, post-baseline value.

For each continuous exploratory endpoint, the change from Baseline will be assessed with a mixed model repeated measure (MMRM) analysis.

For data listings, unless specified, all data will be presented as they have been recorded (e.g. missing and partial dates will not be replaced).

---

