#### 8.6.3.1 Testosterone Normalisation (Primary Definition)

The number and proportion of subjects with normal testosterone levels (testosterone value is between 300-1000 ng/dL inclusive) will be summarised by treatment regimen at each visit using the total testosterone assessed by ICON central lab. Observed values and LOCF values will be presented. In addition, a P-value for the comparison between each dose will be provided using Fisher's exact test.

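### SAP 6.1 makes an MBGS206 lumbar scan a condition of ITT, so men who stop before Week 36 leave the LOCF testosterone analysis and the efficacy and exploratory MMRMs

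*SAP*

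**What the plan says.** **Two definitions of ITT.** Both documents require randomisation and at least one dose. They part on the third condition. Protocol 13.3.1: "Provide a Baseline efficacy value and at least 1 available evaluation of efficacy post-Baseline". SAP 6.1 requires a baseline lumbar-spine value and "at least 1 available evaluation of primary endpoint safety value (lumbar spine) post- Baseline in MBGS206". The mITT set in SAP 6.1.1 is this ITT without site 1156. SAP Section 9 lists three changes from the protocol, and this is not one of them.

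**When the scan exists.** For men who stop early, protocol 12.4 says "DEXA will be performed only if they reached minimum Week 36 (Visit 4) active treatment period". Footnote 11 to SAP Table 1 agrees: "For subjects that discontinued early, EOT DEXA scan will be performed only if they reached minimum Week 36 (Visit 4) active treatment period". SAP 8.6.2 and 8.7.1 both place the MBGS206 scan at EOT only.

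**What runs on ITT.** SAP 8.1.1, 8.6.3 and 8.6.4 assign all secondary efficacy and exploratory endpoints to ITT. For normalisation, SAP 8.6.3.1 says "Observed values and LOCF values will be presented". The LOCF rule in SAP 7.2.1 is that "subjects with a missing observed value at a visit will be imputed with the last non-missing, post-baseline value".

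**What early stoppers contribute.** The row "Testosterone total" in protocol Table 9-1 is marked at Weeks 28 and 32 as well as later. Protocol 9.3.4 adds: "At the time of study drug discontinuation, the subject should have (as soon as possible) an EOT visit", with the Week 48 assessments and within 7 days of stopping.

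**The concern.** A set labelled ITT here selects on staying to Week 36. The men it removes are those whose last values the LOCF rule exists to carry forward, so the rule has least to act on where it is most needed.

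The exclusion can be tied to the outcome. Two consecutive total testosterone values at or above 1500 ng/dL require discontinuation (protocol 9.3.4), while normalisation is capped at 1000 ng/dL (SAP 7.1.3.1). A man stopped on that rule before Week 36 is likely, though not certain, to be out of range at his last value, and he leaves the denominator.

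A reader who sees ITT in a table title will assume the protocol's definition, since Section 9 reports no change.

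**Working it through.** **Step 1: who is excluded.** The only post-baseline MBGS206 scan is at EOT, for men who reached Week 36. The Week 24 scan does not fill the gap. It is transferred from MBGS205 and serves as the MBGS206 baseline. For men who switched from placebo it is also the analysis baseline under SAP 8.1.5. A man who stops before Week 36 therefore cannot meet SAP 6.1, whatever efficacy data he has.

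**Step 2: which analyses change.**

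- Affected: LOCF normalisation (SAP 8.6.3.1, and its mITT repeat in 8.8.4); efficacy summaries at visits before Week 48; the efficacy and exploratory MMRMs (8.6.1, 8.6.3.3, 8.6.4), including any MBGS205 visits those models use.
- Affected only if an early EOT visit is mapped to Week 48: observed-case Week 48 efficacy results, including the one-sample t-tests, and the Week 48 associations in 8.8.3.
- Affected only if SAP 8.1.1 governs: the BMD MMRM in 8.7.1. Section 8.1.1 puts BMD endpoints on ITT and completers, whereas 8.7 puts all safety analyses on Safety. Under 8.1.1, early stoppers' Week 24 scans (window in Appendix F) are lost.
- Not affected: the primary BMD test, which needs an MBGS206 scan under either document (protocol 13.5.2, SAP 8.6.2), and the other 8.7 MMRMs, which use Safety.

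**Step 3: size for LOCF normalisation.** The protocol synopsis gives 30 entrants per previous active arm, about 25 completers and about 17% dropout. These agree: 30 × (1 - 0.17) = 24.9, so about 5 dropouts per arm (30 × 0.17 = 5.1). Their timing is not given. Assume half stop before Week 36: 2.55, that is 2 or 3 men.

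Let k be the men excluded and x the normalised among the 30 - k retained. Let y be the excluded men whose last value is in range (0 to k).

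- Rate on the SAP set: x / (30 - k)
- Rate with them restored: (x + y) / 30

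The retained rates below are assumed.

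| k | SAP set | Restored, y = 0 | Restored, y = k | Change (points) |
|---|---|---|---|---|
| 2 | 27/28 = 96.4% | 27/30 = 90.0% | 29/30 = 96.7% | -6.4 to +0.2 |
| 3 | 26/27 = 96.3% | 26/30 = 86.7% | 29/30 = 96.7% | -9.6 to +0.4 |
| 2 | 23/28 = 82.1% | 23/30 = 76.7% | 25/30 = 83.3% | -5.5 to +1.2 |
| 3 | 22/27 = 81.5% | 22/30 = 73.3% | 25/30 = 83.3% | -8.1 to +1.9 |

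Extreme case: all five dropouts stop before Week 36 and none is last in range. Then 24/25 = 96.0% becomes 24/30 = 80.0%, a change of -16.0. At the other end, if no one stops before Week 36, nothing changes.

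Placebo-switch arm sizes are not given. Assuming 10 men, one early stop and one retained man not normalised, 8/9 = 88.9% becomes 8/10 or 9/10 (-8.9 or +1.1). Assuming 15 men, 13/14 = 92.9% becomes 13/15 or 14/15 (-6.2 or +0.5).

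**The case against.** **The protocol's own Week 48 estimate hardly moves.** Protocol 13.5.1 makes summaries observed-case in general and names no LOCF, and the SAP shows observed values beside LOCF. A man who stops before Week 36 has no observed Week 48 value under either definition unless his EOT visit is mapped there. This stands, and it limits the point to the analyses listed as affected.

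**Outcome-related stops may be rare.** Entrants completed 24 weeks without meeting an MBGS205 discontinuation criterion (protocol 9.3.1, 9.3.2). The earlier study in obese men reported no testosterone peaks above the normal limit among 21 treated men (protocol 7.1.2). This stands for men continuing the same dose. It is weaker for men switched from placebo, who are new to the drug. No document gives a frequency.

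**The loss is visible.** ITT counts and reasons for exclusion are tabulated by regimen (SAP 8.2, 8.3), and baseline characteristics are shown for both Safety and ITT (8.4). This also stands, but a table of exclusions does not restore the rates.

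**Stronger readings a reader might infer.** One is that every MMRM loses these men; SAP 8.7 keeps them in the safety models. Another is that the normalisation rate is inflated. An excluded man may be in range at his last value, so the documents do not settle the direction.

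**Conclusion.** The point holds within the limits above. Followed as written, SAP 6.1 departs from protocol 13.3.1 without saying so and conditions a set called ITT on retention to Week 36.

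On the planning figures, and assuming half the dropouts stop before Week 36, the LOCF normalisation rate in a continuing-active arm could shift by about -10 to +2 points. That range also rests on assumed normalisation rates of about 82% to 96% among retained men, and on each restored man having a value to carry forward. The 17% is a planning figure, not a ceiling.

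The consequence is moderate. All analyses are declared exploratory (protocol 13.5.1, SAP 8.6.1.1). The 75% normalisation criterion appears in protocol 13.5.3.2 but not in the SAP, so no SAP decision rule flips. The definition should still be corrected, because the label misdescribes the set.

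**What to change.** - In SAP 6.1, define the efficacy ITT as protocol 13.3.1 does: randomised, at least one MBGS206 dose, a baseline efficacy value under 8.1.5, and at least one post-baseline efficacy value. If that last value is required to come from MBGS206, list it in Section 9, because the protocol does not say so.
- Give the scan-based set its own name, for example BMD-evaluable, and use it only for the Week 48 one-sample lumbar BMD test.
- Reconcile 8.1.1 with 8.6.2 and 8.7 on the BMD sets. Run the 8.7.1 BMD MMRM on the Safety population so that early stoppers' Week 24 scans are kept.
- List any remaining departure from protocol 13.3.1 in Section 9.

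The cost is SAP wording and one population flag. No new data are needed. Reported rates may move in either direction.

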#### 6.1.1 Modified Intention-To-Treat Population (MITT)

The mITT population includes all subjects who are included in the ITT but were not enrolled from site 1156

Subjects will be analysed according to the treatment to which they were randomised.

### 6.2 Safety population (Safety)

The safety population includes all subjects who received at least one administration of MBGS206 study medication.

Subjects will be analysed according to the treatment actually received. Subjects who did not receive the treatment planned by the randomisation will be analysed according to the treatment received.

#### 6.2.1 Modified Safety Population (MSafety)

The modified safety population includes all subjects who are included in the Safety Population but were not enrolled from site 1156.

Subjects will be analysed according to the treatment actually received. Subjects who did not receive the treatment planned by the randomisation will be analysed according to the treatment received.

### 6.3 Completer Population (CP)

The completer population includes all subjects in the safety population who completed the MBGS206 study and subsequently provided a Week 48 primary endpoint point assessment.

Subjects will be analysed according to the treatment to which they received.

---

### 6.4 PK population

For the summary of semen concentration of BGS649, all subjects who received at least 1 administration of MBGS206 study medication and have at least 1 quantifiable concentration will be included in the PK population.

### 6.5 Other Populations Defined for Tables and Listings

For the purposes of tables and listings a further population will be utilized:

- Randomised population (all randomised subjects)

### 6.6 Protocol Deviations/Violations and Exclusions from Analysis Sets

All violations and exclusions of subjects from analysis populations will be identified and documented at the Classification Meeting prior to study unblinding. The review of each subject's data will be conducted using (but not limited to) the following sources of information:

- Supportive subject listings, provided by the ICON ahead of the Classification Meeting, based on data recorded on the eCRF.
- Protocol Deviation Logs, retrieved from Clinical Trial Management System (CTMS).

## 7 STATISTICAL CONSIDERATIONS AND ANALYSIS

### 7.1 Derived Variables

#### 7.1.1 General Variables

##### Study Day

Study day will be relative to the date of first active study medication (Study Day 1, either from MBGS205 or MBGS206) and calculated as:

- (assessment date – date of first dose of active study medication) + 1, for assessments on or after the date of first dose of active study medication date
- (assessment date – date of first dose of active study medication), for assessments prior to date of first dose of active study medication

##### Follow-up time

Follow-up time (days) will be calculated as:

(date of last contact - date of first dose of MBGS206 study medication) + 1

#### 7.1.2 Definitions relative to demographic and other baseline characteristics

##### Age

Age at informed consent will be calculated as:

Age (years) = (date of informed consent of MBGS205 - date of birth + 1) / 365.25

##### Weight, height and BMI

Weight, recorded in pounds on the eCRF, will be converted in kilograms (1 pound = 0.45359 kg).

Height, recorded in inches on the eCRF, will be converted in centimeters (1 inch = 2.54 cm) (International System of Units).

Body mass index (BMI) will be calculated in kg/m^2 as: weight (kg)/(height (m)).

##### Temperature

Temperature, recorded in Fahrenheit degrees on the eCRF, will be converted in Celsius degrees:

Celsius degrees = (Fahrenheit degrees - 32) x (5/9)

##### HH disease duration

Duration of HH disease will be calculated in years as:

(date of informed consent of MBGS205 – date of initial diagnosis of HH + 1) / 365.25

#### 7.1.3 Definitions relative to efficacy criteria

##### 7.1.3.1 Total Testosterone

##### Testosterone Normalisation

A subject is deemed to have achieved testosterone normalisation if their total testosterone value is between 300-1000 ng/dL (10.4-35 nmol/L) inclusive.

To allow for a potential 10-25% decrease in total testosterone that can occur due to diurnal variation in the afternoons (given current testing is restricted to mornings), a stricter secondary definition of normalisation will be used. A subject is deemed to have achieved the secondary definition of testosterone normalisation if their total testosterone value is between 350-1170 ng/dL (12.15-40.6 nmol/L) inclusive. The secondary definition boundaries were derived by averaging the testosterone value that a 25% decrease in would result in the primary definition boundary with the primary definition boundary itself.

### Testosterone Overshoot

A subject is deemed to have testosterone overshoot if their total testosterone value is greater than 1000 ng/dL (35 nmol/L).

### **7.1.3.2 Body Composition**

#### Gynecomastia

The size of glandular breast tissue, recorded in inches on the eCRF, will be converted in centimeters (1 inch = 2.54 cm).

### **7.1.3.3 International Index of Erectile Function (IIEF)**

The IIEF is a 15-item self-administered questionnaire with each question being scored between 0-5 (see Appendix A - **International Index of Erectile Function (IIEF)** for scoring conversion). Five sexual function domains will be derived by summing the scores of the associated questions (noted in parentheses below):

1. Erectile function (1,2,3,4,5,15)
2. Orgasmic Function (9,10)
3. Sexual Desire (11,12)
4. Intercourse Satisfaction (6,7,8)
5. Overall Satisfaction (13,14)

If at least one of the questions within a domain is missing then the domain will not be calculated. A higher score denotes a higher level of satisfaction/function

In addition the erectile function domain scores will be classified into the below severity categories:

- No Dysfunction (25-30)
- Mild (22-24)
- Moderate (11-21)
- Severe (1-10)

The minimal meaningful difference in the change from baseline in the erectile function domain score is defined as a change in 2 points for subjects who are mild at baseline, 5 points for subjects who are moderate at baseline and 7 points for subjects who are severe at baseline.

### 7.1.3.4 Patient-Reported Outcomes Measurement Information System(®) Sexual Function and Satisfaction (PROMIS(®) SexFS)

The PROMIS SexFS PRO measure will be utilized by collecting a 10 item self-administered questionnaire compiled from relevant items in the PROMIS Sexual Function and Satisfaction domains (Flynn et al., 2013). Each question is scored between 0 and 5 (See Appendix B - **Patient-Reported Outcomes Measurement Information System(®) Sexual Function and Satisfaction (PROMIS(®) SexFS)** for scoring conversion) and three sexual function domains will be derived by summing the scores of the associated questions (noted in parentheses below) and converting to a standardised T-score (standardised to a scale with mean 50 and Standard Deviation 10 – See Appendix B for conversion tables):

1. Interest in Sexual Activity (1,2)
2. Erectile Function (3)
3. Satisfaction with Sex Life (4,5,6,7,8)

If at least one of the questions within a domain is missing then the domain will not be calculated. In addition if a subject answers any question within a domain with a score of 0 (indicating the subject has not had the item in question) then the domain will also not be calculated.

Questions 9 and 10 (Interfering Factors) will be summarized by raw score as no calibration is available for interfering factors.

